each service leaving vacancies for 200 new referrals per year across the three sites. We aim to recruit and randomise 60 participants from across the three sites and have allowed 15 months for recruitment. A main aim of the feasibility trial is to establish whether randomisation to different types of supported accommodation is possible, including its acceptability to service users, clinicians and service providers and its feasibility given the complex logistics involved. A relevant comparison here is with the "Individual, Place and Support" model of supported employment. Though originally considered too logistically challenging for evaluation through randomised controlled trials, such trials have now been carried out successfully (Crowther et al., 2001; Twamley et al, 2003; Burns et al., 2008). Similar challenges may apply here. Service users do not necessarily have much control over the type of supported accommodation they are referred to. Clinicians and providers tend to steer the process and may be anxious about a service user's suitability for one of the two types of supported accommodation we propose to compare. This is not a unique problem in that professionals and clinicians often have opinions that are not evidence based about what is best for their patients. However, we will need to engage with key individuals in each region to agree acceptable protocols. Where there is agreement for a participant to be randomised and they have given their informed consent, they will be randomly allocated on an equal basis to either the supported housing service or the floating outreach service. Randomisation will be conducted independently of the research team by a statistician from the Pragmatic Clinical Trials Unit based at Queen Mary's University London. Randomisation will be stratified by site to ensure equal numbers of participants are allocated to both types of service within and across sites.

COMPARISON SERVICES

Supported housing services provide a constant level of staffing on-site to a number of service users living in individual or shared tenancies with the expectation of move-on within two years. Floating outreach services provide support of flexible intensity to service users living in an independent tenancy which is time-unlimited. Current evidence does not suggest that there are major differences in the content of care and support provided by these two supported accommodation models.

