We will ask those who are recruited whether they have any preference for either of the two models (and if so, which) at baseline. We will also ask the referring clinician if they have any preference for the type of supported accommodation their client receives as part of the staff baseline interview. We will ask the service user and their care coordinator/keyworker to give their feedback about their experiences of randomisation and views about the trial using a simple proforma which will be included in the 12 month follow-up interviews. In addition, we will ask other key individuals involved in the supported accommodation referral process to give their feedback using the same proforma.

We will ask service users who do not wish to be randomised (and clinicians who do not agree for their service users to participate) their reasons for this. We will invite up to 60 service users in this group to participate in a naturalistic follow-up to determine their outcomes over time. If they are willing, we will collect the same baseline and outcome data as for randomised participants from staff and service users.

Baseline assessment

Before randomisation we will collect data on participants' age, gender, ethnic group, diagnosis, length of contact with mental health services and previous type of accommodation from staff and case notes. We will also assess their social function using the staff rated Life Skills Profile (Parker et al., 1991) and adjust for this in our analyses.

12 month outcome assessment

We will test the feasibility of collecting the following outcomes for service user participants at 12 months follow-up. These outcomes include those suggested by staff and service users in our previous qualitative study and those suggested in the background section of this protocol. Where relevant, assessments will be carried out at baseline as well as 12 month follow-up (denoted by *) in order to assess for baseline scores and adjust for these in our analyses. Where we have more than 30% missing data we will consider that outcome to be unfeasible to include in a larger trial. If there is more than 10% missing data for any outcome (but less than 30%) we will consider if there are ways to improve the response rate.

From service user interviews:

- Mental health (**Brief Psychiatric Rating Scale*** [Overall and Gorham, 1962])
- Quality of Life (**Manchester Short Assessment of Quality of Life*** [Priebe et al., 1999])

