Given that the researchers will need to visit the services to collect follow-up data it may not be possible for them to remain masked to participant allocation. However, many of our likely outcomes are objective and independent of potential rater bias. We will explore the feasibility of using a telephone interview to collect follow-up data from service users, conducted by a second researcher who remains blinded to the participant's allocation. This would involve the site researcher visiting the participant at their supported accommodation/home and taking informed consent for the follow-up interview. They would then telephone a second researcher based at the research office who would then complete the interview with the participant.

LIKELY RATE OF LOSS TO FOLLOW-UP

It is unlikely that we shall lose many service users to follow-up due to the high support they receive from services. However, many of our outcomes are assessable from case notes and staff rated measures so that if a service user is not contactable we will be able to gather some outcome data. We will seek consent for this at recruitment.

STATISTICAL ANALYSIS

We shall follow CONSORT guidelines on the analysis of randomised trials for the presentation of our results (or the CONSORT extension for pilot/feasibility trials if these are published by the time we publish). However, our analysis will be mainly descriptive and will focus on the recruitment rate, acceptability of randomisation to participants and staff, ease of collection of data, characteristics of participants, other baseline and outcome variables, the feasibility of masking outcome assessments, loss to follow-up and any adverse events. We shall provide a descriptive analysis of our principal outcomes and assess the potential for combining them in one multivariate analysis in a main trial. Although we do not expect any statistically significant difference in our outcomes, the confidence intervals of our estimates will assist in calculating power and sample size for a full trial.

COST EFFECTIVENESS

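### Site is the only stratification factor, but the stated adjustments leave it out, so the intervals meant for main-trial sizing would be slightly too wide

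*Protocol*

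**What the plan says.** Three parts of the protocol bear on this.

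- **Allocation of Participants to Trial Arms.** Once consent is given, "they will be randomly allocated on an equal basis to either the supported housing service or the floating outreach service". The method is given in one sentence: "Randomisation will be stratified by site to ensure equal numbers of participants are allocated to both types of service within and across sites". A trials-unit statistician outside the research team carries it out. No blocking or other restriction is named.
- **Outcome Assessments.** Adjustment is stated twice. Under Baseline assessment: "We will also assess their social function using the staff rated Life Skills Profile (Parker et al., 1991) and adjust for this in our analyses". Under 12 month outcome assessment, the starred measures are taken at both times "in order to assess for baseline scores and adjust for these in our analyses". Site appears in neither place, and neither sentence says the list is complete.
- **Statistical Analysis.** The section says that "our analysis will be mainly descriptive and will focus on the recruitment rate, acceptability of randomisation to participants and staff". It adds that "the confidence intervals of our estimates will assist in calculating power and sample size for a full trial".

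**The concern.** When allocation is balanced within site, differences between sites cannot contribute to the difference between arms. The true sampling variance of that difference is therefore free of between-site variance. A model without site does not use this: it leaves the between-site spread in the residual, and the standard error is too large. The usual remedy is to analyse by the factor used in the randomisation.

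It matters here because the intervals have a stated later use, the power and sample size of the full trial. An inflated residual variance would pass into that calculation. The protocol also gives some reason to expect sites to differ. Its Background says that provision and costs follow local tradition and housing stock, and the sites are two parts of London plus a third location outside it.

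**Working it through.** **Figures in the plan.** The protocol gives no standard deviation, effect size, alpha or power, so the target of 60 is a recruitment target and cannot be re-derived. The one calculation beside it does reproduce: 0.20 × 1000 = 200 vacancies a year.

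**Inputs.**
- From the protocol: 60 participants, three sites, 1:1 allocation, stratified by site.
- Assumed: about 20 participants per site.
- Assumed: site explains a share ρ of outcome variance, from 0.01 to 0.10. The relevant share is what remains after the baseline adjustments already promised.

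**Step 1: interval width without site, under balanced stratified allocation.** The unadjusted standard error uses the total variance and the adjusted one uses (1 − ρ) of it. The width ratio is 1/√(1 − ρ), and the ratio of the resulting sample sizes is 1/(1 − ρ).

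| ρ | Width ratio | Sample size ratio |
|---|---|---|
| 0.01 | 1/√0.99 = 1.005 | 1.010 |
| 0.02 | 1/√0.98 = 1.010 | 1.020 |
| 0.05 | 1/√0.95 = 1.026 | 1.053 |
| 0.10 | 1/√0.90 = 1.054 | 1.111 |

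**Step 2: coverage by simulation.** The set-up was 20 per site, blocks of 4, a linear model and 6,000 runs per setting.

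| ρ | 95% coverage without site | 95% coverage with site | Mean width without / with site |
|---|---|---|---|
| 0.02 | 0.952 | 0.953 | 1.023 / 1.018 |
| 0.05 | 0.956 | 0.948 | 1.021 / 1.003 |
| 0.10 | 0.962 | 0.948 | 1.017 / 0.977 |

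The unadjusted intervals are valid to slightly conservative. The simulated width ratios (about 1.005, 1.019 and 1.041) fall a little below the formula. With only three randomly drawn sites, the realised between-site spread is on average smaller than the nominal share.

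**Step 3: scale.** A standard deviation estimated with 60 − 2 = 58 degrees of freedom has a 95% interval that puts the planned sample size anywhere between 58/χ²(0.975) = 0.72 and 58/χ²(0.025) = 1.49 times its estimate. The 1% to 11% from omitting site is small against that.

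**Step 4: the equal-numbers wording.** Separate lists per site, with no restriction inside each list, amount to simple randomisation. With 20 per site:
- P(10:10 in one site) = C(20,10)/2²⁰ = 0.176.
- P(10:10 in all three) = 0.176³ = 0.0055.
- P(35:25 or worse overall) = 0.25.

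Imbalance of that order costs little. The standard error ratio √[(1/35 + 1/25)/(1/30 + 1/30)] is 1.014. With blocks of 4 inside site (an illustrative size), the difference in any site is at most 2. Even a restricted scheme therefore gives near-equality and not exact equality.

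**The case against.** The strongest reply is that the protocol nowhere excludes site. Each adjustment is mentioned where its measure is introduced. Neither sentence is a model specification, and a full covariate list belongs in an analysis plan that is not shown here. That stands as far as it goes. A reader might infer that the intervals will ignore the design, and the document does not support so firm a statement. It supports only this: the adjustments the protocol commits itself to omit the factor it randomises by.

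A reader might also infer that allocation is unrestricted and that marked imbalance is likely. The protocol does not say so. Its stated aim of equal numbers within site, carried out by a trials-unit statistician, points towards restriction, and block sizes are often withheld on purpose. The probabilities in Step 4 show only that stratification by itself cannot deliver what the sentence promises.

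The two readings cannot be combined. The excess width in Step 1 requires balance within site. If allocation were unrestricted, the unadjusted interval would be right for that design: simulated coverage without site was 0.952, 0.952 and 0.952 at ρ of 0.02, 0.05 and 0.10.

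Two further objections hold. Any error is in the safe direction. And a fixed site effect in every between-arm estimate is too much to ask, because some outcomes, such as eviction or loss of tenancy, may have few events with about 30 people per arm. The fix is limited accordingly.

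**Conclusion.** The point holds as a modest correction. The protocol commits to an adjustment set without its only stratification factor, and it sends the resulting intervals forward to size a full trial. On the stated text those intervals would be about 0.5% to 5% too wide, and a sample size drawn from them about 1% to 11% too large.

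This rests on four assumptions: balance is achieved within site; site explains 1% to 10% of outcome variance; the outcomes are continuous and analysed by a linear model; and the full trial would itself analyse by site. The range for site is not in the protocol, and baseline adjustment may absorb part of it.

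Nothing here threatens the study's main conclusion. Feasibility is judged on recruiting 60 people in 15 months, which depends neither on balance between arms nor on the covariates in a model. The wording on equal numbers is a minor matter.

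**What to change.** - **12 month outcome assessment.** Extend the adjustment sentence for continuous outcomes with: 'and for site, the stratification factor'. For binary outcomes, include site only where event numbers allow. The cost is 2 degrees of freedom (58 to 56 before other covariates), with no new data.
- **Allocation of Participants to Trial Arms** (minor). Either state that allocation is restricted within site, with block sizes not disclosed to the research team, or replace the promise of equal numbers with 'to promote balance'. This changes one phrase and need not alter the procedure.

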There have been no trials investigating the effectiveness of supported accommodation services for people with mental health problems (Chilvers et al., 2002) and other types of studies investigating these services are few and poor in quality (Fakhoury et al., 2002). The paucity of research reflects the logistic difficulties in researching this area. Randomisation to different types of housing support may be resisted by clinicians who feel that service users require a staged process, moving from higher to lower supported settings as their skills and confidence increase, and by service users with clear preferences for particular services. It also seems that the availability of supported housing stock is more influential than clinical need in determining accommodation allocation.

These clinical and housing constraints mean, however, that we simply do not know whether or not individuals are following the most cost effective routes to independence. In short, we do not know whether more tailored support delivered to service users in their own homes through floating outreach is more acceptable, more individualised and more cost-effective than a standard level of support provided in staffed facilities. However, in the US, the “Train and Place” approach (which provides a constant level of staffing on-site to a number of apartments with the expectation of service users moving-on as they gain independent living skills) has been compared in a quasi-experimental study to the “Place and Train” approach (which provides floating outreach support of flexible intensity to service users living in an independent, time-unlimited tenancy) and found to facilitate greater community integration and service user satisfaction (Corrigan et al., 2005).

In summary, there is no clear evidence as to whether the supported housing model (offering time limited, building based support) is more or less effective than the floating outreach model (offering flexible, visiting support to people in a permanent independent, tenancy). This clinical equipoise therefore justifies assessment through a randomised controlled trial, but, given the logistic difficulties outlined above, there is first a need to assess the feasibility of conducting such a trial.

OBJECTIVE

This study aims to assess the feasibility of a randomised evaluation of two models of supported accommodation for people with mental health problems.

DESIGN AND SETTING

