The **content of care delivered by both types of service** will be assessed during the feasibility trial 6 and 12 months after participant randomisation using:

- a) a standardised quality assessment tool completed by the supported accommodation service manager through a face to face interview with the researcher. This tool was developed by the authors and subsequently adapted for supported accommodation services during an earlier phase of this programme of research (QuIRC; Killaspy et al., 2010). Managers will also be asked to complete a proforma to provide descriptive data on the service. We will complete these tools once for each service, 6 months after the first participant is randomised to that service.
- b) a proforma to collect information about the number of contacts made by staff of the supported accommodation service with service users over the previous 3 months. This information will be collected from service users and corroborated with staff and case note review 6 and 12 months after randomisation.
- c) a standardised measure that assesses the amount and complexity of activities service users have engaged in over the previous week (the Time Use Diary, Jolley et al., 2006). This measure will be completed separately by a staff member who knows

the participant well (such as the participant's keyworker) and the participant through face to face interviews with the researcher, 6 and 12 months after randomisation.

OUTCOME ASSESSMENTS

The main aim of this study is to assess the feasibility of a large scale randomised controlled trial assessing two existing models of supported accommodation. We will therefore assess a number of aspects of feasibility: the number of referrals to the trial; the number recruited and randomised; attrition (i.e. the number who withdraw consent to continue with the research, decline to move to the allocated service, or cannot be located at follow-up); and the time from recruitment to moving into either type of supported accommodation. Data on these areas of uncertainty will inform the feasibility of a larger scale trial including the rate at which recruitment could take place and the likely number of sites required. If we are able to recruit our target of 60 participants (who would all be randomised) from three sites over our 15 month recruitment period then we will consider a large scale trial to be feasible.

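### The one trial-level decision rule calls a large trial feasible once 60 are randomised in 15 months, whatever share take up the accommodation they were allocated

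*Protocol*

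**What the plan says.** Under Outcome assessments the protocol lists what it will measure to judge feasibility. Besides how many are referred and how many enter the trial, one item is "attrition (i.e. the number who withdraw consent to continue with the research, decline to move to the allocated service, or cannot be located at follow-up"). Another item on the list is "the time from recruitment to moving into either type of supported accommodation". It adds: "Data on these areas of uncertainty will inform the feasibility of a larger scale trial including the rate at which recruitment could take place".

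The same paragraph ends with the decision rule. Its condition is that the target of 60 is met, with everyone who is recruited going on to allocation. The verdict follows if that number comes "from three sites over our 15 month recruitment period then we will consider a large scale trial to be feasible". Uptake, attrition and time to moving in have no threshold and do not appear in the rule.

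Two other sections bear on what the rule ought to test. Allocation of participants to trial arms states the aim: to establish "whether randomisation to different types of supported accommodation is possible, including its acceptability to service users, clinicians and service providers", and also its feasibility in view of the logistics. The Background warns that "the availability of supported housing stock is more influential than clinical need in determining accommodation allocation".

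The only other numerical criteria are the 30% and 10% missing-data limits under 12 month outcome assessment. They decide whether a single outcome measure is kept or its response rate improved, not whether a trial is feasible.

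**The concern.** Randomising someone and placing that person in the allocated accommodation are separate events here. Resistance from clinicians or service users may show before randomisation, and a count of those randomised captures it. A missing vacancy, a long wait or a refusal to move shows after randomisation, where the rule does not look. The protocol names housing stock and logistics as obstacles, yet a study that randomised 60 people and placed few of them as allocated would still meet its stated definition of success.

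At stake is the answer to the study's single objective. A full trial launched on that verdict could have too little separation between its arms to answer its question at the planned size.

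**Working it through.** **The plan's own figures.** Allocation of participants to trial arms gives over 1000 service users and an average 20% moving on each year. 0.20 × 1000 = 200 vacancies a year, as stated. Over 15 months this is 200 × 15/12 = 250, so the target of 60 is 60/250 = 24% of vacancies. The 200 is a total over both types of service, so it does not show that a place of the allocated type will be free for a given participant. The target of 60 has no stated power or precision behind it to reproduce.

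**What the rule returns.** Inputs: number randomised, number of sites, recruitment period. Uptake is not an input. With 60 randomised in time, the result is feasible at 0/60, 30/60 or 60/60 in the allocated type.

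**What low uptake would cost a full trial.** Assume that those who do not take up their allocation contribute no between-arm difference. The intention-to-treat difference is then uptake × the full difference. Required size varies with 1/(difference)², so it is multiplied by 1/uptake². The protocol gives no expected uptake, so a range is shown. The last column is for scale only and assumes a standardised difference of 0.3, 90% power and two-sided 5%; none of these is in the protocol. It uses n per arm = 2(1.960 + 1.282)²/(0.3 × uptake)², rounded up.

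| Uptake (assumed) | 1/uptake² | Total N |
|---|---|---|
| 100% | 1.00 | 468 |
| 90% | 1.23 | 578 |
| 80% | 1.56 | 730 |
| 70% | 2.04 | 954 |
| 50% | 4.00 | 1868 |

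The present rule passes every row.

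**Whether 60 participants can support an uptake criterion.** Take at least 42 of 60 (70%) purely as an illustration. The chance of passing is P(X ≥ 42) with X binomial(60, true uptake):

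| True uptake | Chance of passing |
|---|---|
| 50% | 0.001 |
| 60% | 0.072 |
| 70% | 0.563 |
| 80% | 0.978 |

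So 60 participants separate poor from good uptake well, but not values close to the threshold. Exact 95% intervals: 30/60 gives 37% to 63%, 42/60 gives 57% to 81%, 48/60 gives 68% to 89%. One arm of 30 is much less precise: 21/30 gives 51% to 85%.

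**What the planned data would show.** The attrition measure pools refusal to move with research withdrawal and loss to follow-up. It counts those who decline, and does not name those never placed for lack of a vacancy. Time to moving in refers to either type of accommodation, not the allocated type. As defined, these measures do not directly give the proportion placed as allocated.

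**The case against.** The best defence is that uptake is in view. Refusal to move is counted, and the sentence just before the rule says such data will inform feasibility. Preferences at baseline, feedback at 12 months, the qualitative interviews and the descriptive analysis all bear on acceptability. The count randomised also speaks directly to the stated aim: "A main aim of the feasibility trial is to establish whether randomisation to different types of supported accommodation is possible". Analysis is mainly descriptive, and anyone deciding on a full trial would see the uptake data.

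Most of this stands, and it limits the point. A reader might infer that the protocol ignores uptake. It does not: uptake is partly recorded, and what is missing is a threshold and a place in the rule. The defence does not remove the conflict, because the next sentence gives an unconditional verdict on the count. If recruitment succeeds and uptake fails, the two sentences point in different directions. The missing-data limits do not help either. They apply to each outcome, and Likely rate of loss to follow-up says many outcomes can come from case notes and staff ratings, so data may be complete for people who never moved.

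A reader might also infer that the target of 60 is close to a coin toss, because 60 in 15 months is 4 a month. The documents do not support that. The protocol states no expected recruitment rate, and 4 a month is only the target divided by the period.

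**Conclusion.** The point holds in a limited form. The protocol fixes a trial-level rule that can return the wrong answer to its only objective, because uptake of the allocation is not part of it. The possible cost is a full trial 1.56 times larger at 80% uptake, 2.04 times at 70% or 4 times at 50%, provided that those who do not take up their allocation contribute no between-arm difference. Crossover into the other type of service would give different figures.

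A reader might infer that a full trial would in fact need four times the participants. The documents give no basis for 50% or any other uptake; the range shows what the rule would let through, not what is likely.

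This should be fixed, but it is not a fatal fault. No effect estimate is biased and no participant is put at risk. The uptake information that is recorded would be available before a full trial began.

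**What to change.** Rewrite the last sentence of the feasibility paragraph under Outcome assessments as a joint rule:

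- A large trial is considered feasible if 60 participants are randomised from three sites in the recruitment period, **and** at least a pre-set proportion of them move into the allocated type of service within a pre-set time. The sponsor chooses both values before results are known. The 42 of 60 above is illustrative and is not taken from the protocol.
- If 60 are randomised but uptake falls short, the conclusion is only that recruitment is feasible.
- Uptake is reported overall and by arm with 95% confidence intervals. The criterion is best applied overall, since about 30 per arm gives wide intervals.
- Refusal to move and non-placement for lack of a vacancy are counted separately from each other, and both separately from research withdrawal and loss to follow-up. Time to moving in is recorded for the allocated type.

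The cost is one paragraph of protocol text and explicit recording of the type of accommodation each participant enters, and when. The disadvantage is that success becomes harder to claim, and that true uptake close to the chosen level could pass or fail by chance.

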We will carry out in-depth qualitative interviews with 10 participants and 10 key staff involved in the referring process (e.g. referrals coordinators, referring clinicians and supported accommodation staff) to assess their experiences of the trial including the process of randomisation, and their views on the usefulness and feasibility of a larger scale trial. Interviews will be recorded, independently transcribed and anonymised. The text data will be entered into a software package (Atlas-ti) to assist management and coding. A coding frame will be developed by one of the researchers with supervision from SP and GL. The main topics included in the interview prompts will be used as the basis for the coding frame which will then be expanded and modified to include further codes as new themes and sub-themes emerge in the course of interviews and analysis. A detailed and comprehensive analysis strategy will be agreed at the early stages of data collection. However, it is not our intention to produce overly interpretative accounts of the experiences of service users and staff, rather to systematically elicit and detail common themes that will inform the feasibility of a larger trial.

A sample of service user and staff transcripts will be randomly selected and re-coded by a second researcher to assess the validity and correlation of coding. Agreement will be considered to have occurred if both coders used the same code(s) for a paragraph of text.

Analysis will be informed by the principles and guidelines for quality in qualitative research (Spencer et al., 2003). A full report detailing the coding and thematic development, alongside a comprehensive list of quotations and exemplars, will be made available.

DATA MANAGEMENT

Data will be entered onto a purpose designed database by the researchers. Data management will be according to the Barts and the London Pragmatic Clinical Trials

Unit (PCTU) Standard Operating Procedures. Data checking and cleaning will be carried out by the junior statistician in conjunction with the researchers. Cleaned data will be transferred to Stata statistical software for analysis at PCTU. All paper data will be stored in locked filing cabinets and electronic data will be password protected. Once analysis is complete all superfluous paper data will be shredded and appropriate data will be stored in Barts and The London archives for 20 years.

MASKING OF RESEARCHERS

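### The only acceptability measure planned for every randomised user is a proforma at 12 months, so it misses users who leave earlier and may overstate how acceptable randomisation was to users

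*Protocol*

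**What the plan says.** Allocation of Participants to Trial Arms makes it a main aim to find out whether randomisation is possible, "including its acceptability to service users, clinicians and service providers". Statistical Analysis lists "acceptability of randomisation to participants and staff" among the topics on which the mainly descriptive analysis will concentrate.

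Outcome Assessments describes the measure: "We will ask the service user and their care coordinator/keyworker to give their feedback about their experiences of randomisation", together with "views about the trial using a simple proforma which will be included in the 12 month follow-up interviews". It adds that "we will ask other key individuals involved in the supported accommodation referral process to give their feedback using the same proforma", with no time point given for these respondents.

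The same section treats attrition as a feasibility outcome, defined as "the number who withdraw consent to continue with the research, decline to move to the allocated service, or cannot be located at follow-up". It plans a count and mentions no reasons. Reasons are sought only from users who do not want to be randomised and from clinicians who do not agree to their users taking part.

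A second source is under Qualitative Evaluation: "We will carry out in-depth qualitative interviews with 10 participants and 10 key staff involved in the referring process". These interviews cover the process of randomisation. Timeframe places them in months 31-40, with recruitment in months 31-44 and 12-month follow-up in months 41-54.

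**The concern.** A user who reacts badly to the allocation has a reason to leave, and leaving removes that user from the 12-month proforma. Whether an answer is missing may therefore depend on what the answer would have been. The protocol supplies the mechanism: its Background expects some users with clear preferences to resist randomisation, and users' preferences are recorded at baseline. The statement under Likely Rate of Loss to Follow-Up that few users will be lost rests on the support they receive from services. It does not consider withdrawal because of the allocation.

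Timing matters even without attrition. Completers look back a year, after living with the result, in the interview that also rates satisfaction with the service.

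What is at stake is the report on one of the trial's main aims. The timing is a data-collection choice fixed in the protocol, and no later analysis can recover answers that were never collected.

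**Working it through.** The protocol states no acceptability rate and no attrition rate, so there is no figure to reproduce. The check has three parts.

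**1. Which sources reach a user who leaves after randomisation**

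| Source | Reaches a user who withdraws or is lost before 12 months? |
|---|---|
| User proforma at 12 months | No |
| Reasons for refusing | No; asked only of users not willing to be randomised and of clinicians who do not agree |
| Attrition count | Yes, as a number without a reason |
| Keyworker proforma at 12 months | Possibly, but it gives the staff view |
| Case-note and staff-rated outcomes for users who cannot be contacted | Possibly, but not the user's own view of randomisation |
| In-depth interviews, months 31-40 | Only if the user is one of the 10 |

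**2. How far the 10 interviews close the gap**

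Inputs: 60 randomised (Allocation of Participants to Trial Arms) and 10 interviewed (Qualitative Evaluation). The sampling method is not stated; assume a simple random sample of the 60. If m users later leave, the chance that at least one of them is interviewed is 1 − C(60−m, 10)/C(60, 10), and the expected number is 10m/60.

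- m = 3: chance 43%, expected number 0.5
- m = 6: chance 68%, expected number 1
- m = 12: chance 91%, expected number 2

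The interviews are likely to include a future leaver if attrition is appreciable, but only one or two. The interview window also closes in month 40, before recruitment ends in month 44, so users randomised after month 40 cannot be interviewed within it.

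**3. Size of the possible overstatement**

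Let d be the proportion lost by 12 months, and p_c and p_l the proportions of completers and leavers who find randomisation acceptable.

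- Proportion among all randomised = p_c(1 − d) + p_l·d
- Proportion seen at 12 months = p_c
- Overstatement = p_c − [p_c(1 − d) + p_l·d] = d(p_c − p_l)

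None of the three values is in the protocol. As an illustration take p_c = 80%. For d = 20% and p_l = 20%, the proportion among all randomised is 0.80 × 0.80 + 0.20 × 0.20 = 0.68, an overstatement of 12 points. The range, in percentage points:

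| Lost (of 60) | p_l = 80% | p_l = 50% | p_l = 20% |
|---|---|---|---|
| 5% (3) | 0 | 1.5 | 3 |
| 10% (6) | 0 | 3 | 6 |
| 20% (12) | 0 | 6 | 12 |
| 30% (18) | 0 | 9 | 18 |

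For scale, the 95% confidence half-width for a proportion of 80% is 1.96 × √(0.8 × 0.2/60) = 10 points with 60 respondents and 11 points with 48. At low attrition the overstatement is well inside sampling error. At 20% to 30% loss with strongly different views it matches or exceeds it.

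**The case against.** The strongest reply is that acceptability has several sources. The interviews start during recruitment and before follow-up opens, so they reach some users without a full year's hindsight. Withdrawal, refusal to move and non-location are counted for everyone randomised, so leaving is visible. Nothing stops a user who declines the allocated service but stays in the research from being asked at 12 months. Keyworkers and referral staff also give feedback, and baseline preference allows attrition to be described by whether the allocation matched it. All of this stands. What it does not supply is the reason why a randomised user left.

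A reader might infer that users who leave are captured nowhere. The interviews and counts show otherwise. A reader might also infer that acceptability is certain to look better than it is. The documents do not support that either: leavers may think as completers do, and hindsight after a poor placement could lower the rating.

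Nor does the proforma enter the stated feasibility rule, which is recruitment of 60 participants from three sites in 15 months. Changing its timing would not alter that decision.

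Finally, the proforma is described as simple feedback and no summary proportion is specified, so the figures above only illustrate scale. The 12-month point is sensible for views on the trial as a whole, because moving in takes time. It is less suited to views on being randomised.

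**Conclusion.** The point holds in a limited form. The one acceptability measure meant for all randomised users is taken at 12 months. It omits users who withdraw or cannot be located before then, and it asks the others to recall randomisation a year later. The remaining sources offset this only in part, because no reasons are sought from users who leave after randomisation.

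User acceptability may therefore be overstated, by an unknown amount equal to d(p_c − p_l). It is zero if leavers and completers hold the same views. In the illustration it runs from 0 to 18 points, assuming 80% acceptability in completers, 20% to 80% in leavers and 5% to 30% lost. If few are lost, as the protocol expects, it stays at the low end: at most 6 points at 10% loss.

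The consequence is for the reported result on a main aim, not for the recruitment-based feasibility rule. The change is worth making because it is cheap and the missing answers cannot be recovered later.

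**What to change.** - Give the randomisation items of the user proforma soon after the user learns the allocation, or at the 6-month face-to-face interview already planned under Comparison Services for the Time Use Diary. The earlier point is better, since a 6-month form still misses users who leave before it.
- When a user withdraws or declines to move to the allocated service, invite a reason. Make clear that answering is voluntary.
- Keep the 12-month form for views on the trial as a whole.
- Report user acceptability against all randomised users, with leavers and any reasons they give shown separately.

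The cost is protocol wording, one more short form at or near an existing contact, and one optional question at withdrawal. Some leavers will not answer, so the gap narrows but does not close.
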